8.4.6 Serious Adverse Event Reporting

Members of the study team will record all reportable events within 24 hours of knowledge of the SAE with start dates occurring any time after informed consent is obtained until 30 days after the last day of study participation. At each study visit, the investigator will inquire about the occurrence of SAEs since the last visit. Events will be followed for outcome information until resolution or stabilization.

The Investigator will categorize the **outcome** of each SAE according to the definitions below:

Resolved: The subject recovered from the AE.

Ongoing: At the time of the last assessment, the event is ongoing, with an undetermined outcome. Note: Ongoing AEs are not considered resolved as a result of death. No AE stop date should be recorded with an AE that is ongoing.

Chronic/Stable: At the time of the last assessment, the event is ongoing and stabilized, with no change to the event outcome anticipated.

Death: The AE directly caused death.

Unknown: There is an inability to access the subject or the subject's records to determine the outcome (ie, subject withdraws consent or is lost to follow-up).

Definitions:

Death: Any event resulting in a subject's death must be reported as an SAE. However, death, in and of itself, is not an AE; it is only an outcome. The cause of death is the AE. Therefore, the investigator should make every effort to obtain and document the cause of death for all subjects who die during the study. If, despite all efforts, the cause of death remains unknown, the AE should be documented as an "unspecified fatal event".

Life threatening AE: Any AE that places the patient or subject, in the view of the investigator, at immediate risk of death from the reaction as it occurred (ie, it does not include a reaction that, had it occurred in a more severe form, might have caused death).

Hospitalization: It should be noted that hospitalization, in and of itself, does not represent an SAE. It is the AE leading to the subject's hospitalization that becomes "serious" when it requires inpatient care. Consequently, an SAE should not be reported in the case of pre-planned hospitalizations for pre-existing conditions that did not worsen during the study.

Dalcinonacog alfa_DLZ-201 VERSION 2.0, Amendment 1

Disability: A substantial disruption of a person's ability to conduct normal life functions.

8.4.7 Adverse Events of Special Interest (AESIs)

The study drug has the potential risk of causing the following AESIs based on information associated with other drugs in the same category. These are:

1. Thromboembolic events (TEs) based on information associated with other drugs for treatment of hemophilia. TEs include myocardial infarction (MI); venous thrombosis, and pulmonary embolism (PE); and stroke. See **Appendix A** for signs and symptoms listed for the subjects and the study team personnel as those requiring urgent reporting and attention.
2. Immune response resulting in antibody formation and potentially an inhibitory antibody response. This will also be monitored for throughout the study.

8.4.8 Reporting of Pregnancy

Although pregnancy itself is not considered an adverse event or a serious adverse event, the partner of a male participant should be followed until termination or to term to ensure absence of congenital anomaly or birth defect that may have resulted from maternal exposure or transmission of the study drug via semen following paternal exposure.

All participants must be advised to use a highly effective method of birth control from the first dose of study drug through 28 days after dosing to protect the health and safety of the mother and/or child. Despite the warnings provided and precautions taken, pregnancy may occur during research participation. Investigators must be aware of the requirements related to reporting and follow-up in the event a research participant's partner becomes pregnant.

If a participant's partner becomes pregnant during this study, please provide an authorization form to present to the partner. If she is in agreement, that authorization will function as consent to approve the study doctor's access to medical information to allow the regulatory required monitoring of the pregnancy, and the birth and the health of the child.

Please report the pregnancy of a participant's partner to Catalyst Biosciences, or its designee, and the IRB, and include the following information: expected date of delivery, last menstruation, estimated conception date and pregnancy result (if known).

Dalcinonacog alfa_DLZ-201 VERSION 2.0, Amendment 1

Pregnancy should be reported as "Information" (not as an "Adverse Event" or "Other Problem or Event").

- Pregnancy does NOT have to be reported to the IRB if the subject is receiving follow-up only, and conception occurred outside of the time period that the study protocol requires contraception (ie, 28 days after the last dose of the study drug and the pregnancy occurred after that time).
- Subsequent reports containing follow-up information regarding a pregnancy is not required unless the pregnancy results in a congenital anomaly. The congenital anomaly should be promptly reported.
- NOTE: If you suspect that exposure to a medical product prior to conception or during pregnancy may have resulted in an adverse outcome in the child, it must be reported to the Food and Drug Administration (FDA).

Dalcinonacog alfa_DLZ-201 VERSION 2.0, Amendment 1

9. STATISTICAL CONSIDERATIONS

9.1 STUDY HYPOTHESIS

The study hypothesis is that a daily SC dose of CB2679d results in levels sufficient to provide protection from spontaneous bleeding.

Primary Analysis Plan:

Appropriate descriptive statistics of all measured parameters will be reported, including 95% confidence intervals.

The dose required to achieve steady-state levels >12% will be reported for daily dosing, including 95% confidence intervals.

Primary Endpoint

The primary endpoint will include:

- Number of subjects who achieve a steady-state FIX activity level above 12%, with daily dosing.

Secondary Endpoints

The secondary endpoints will include:

- Safety assessments: Occurrence of antibody formation resulting in a decreased endogenous level of FIX; occurrence of a clinical thrombotic event not attributable to another cause.
- Occurrence of a conformed antibody response with high titer to CB2679d and whether it is inhibitory and cross-reactive to BeneFIX®.
- Change in FIX activity levels.
- Occurrence of clinically significant levels of thrombogenicity markers resulting from SC administration of CB2679d.

Dalcinonacog alfa_DLZ-201 VERSION 2.0, Amendment 1

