Interim results showed PK and activity of CB2679d as 22-fold greater potency over BeneFIX® and longer mean residence time. Single-dose bioavailability was 18.2-23.6%, SC beta $t_{1/2}$ was 66-103 hours and time that CB2679d is present at the maximum concentration in serum (T_{max}) was 6-24 hours. One subject reported transient fever and a mild SC injection site reaction. Cohort 4 was omitted as sufficient data had been gained from single dosing SC in Cohorts 2 and 3. The SC dose in Cohort 5 was reduced from 300 IU/kg to 150 IU/kg daily. PK and activity

Dalcinonacog alfa_DLZ-201 VERSION 2.0, Amendment 1

levels after 6 daily doses in 5 subjects reached a median of 15.7% [interquartile range 14.9% to 16.6%] Four of 5 subjects had levels above 12%. Half-life was 63.2 hours [interquartile range 60.2 to 64.0 hours]. The interim study results support the aim of achieving normal or high mild hemophilia FIX levels in individuals with hemophilia B with repeated SC dosing. Mild pain, erythema and redness was reported at the injection site in initial injections and not a later injection. One subject reported these adverse events to be moderate for the first 2 injections and mild thereafter. An IV loading dose has been added to cohort 6 in this study to see if it eliminates injection site adverse events as they are believed to be due to low FIX levels because of washout of prior treatment ([Figure 2](#)).

The nadir activity after IV plus SC dosing was 20% in both subjects in cohort 6 and thereafter levels increased to >30%. It is clear that the IV loading dose increased the bioavailability of SC CB2679d by increasing the saturation of the extravascular compartment and resulted in greater activity levels than simple addition of SC to IV activity. Neutralizing antibodies developed in both subjects (transiently in one subject). A root cause analysis determined that the most likely cause was a 3-month gap between dosing in cohort 5 and cohort 6 in these 2 participants ([Figure 3](#)).

FIGURE 2. CB2679D PHASE 1/2 OPEN LABEL STUDY DESIGN

[figure not shown]

IV, intravenous; SC, subcutaneous.

^aFirst SC dose 30 minutes post-IV.

Dalcinonacog alfa_DLZ-201 VERSION 2.0, Amendment 1

FIGURE 3. CB2679D PHASE 1/2 STUDY: COHORT 5 & 6 FIX ACTIVITY RESULTS

Dalcinonacog alfa_DLZ-201 VERSION 2.0, Amendment 1

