3. OBJECTIVES

3.1 PRIMARY

The primary objective is:

- To evaluate the dose required to achieve steady-state FIX levels >12% of a SC prophylaxis treatment regimen of CB2679d, in adult subjects with hemophilia B.

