9.2 SAMPLE SIZE DETERMINATION

6 subjects are sufficient to provide guidance on range of dose required to achieve steady-state activity >12% and starting SC dose for subsequent studies. As this study is not inferential, no formal sample size calculation is required.

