9.4 STATISTICAL ANALYSIS

9.4.1 General Approach

Various pharmacokinetic parameters will be calculated, including area under the time curve (0-t and 0-infinity), clearance, volume of distribution at steady-state, T_{max} and C_{max} , and terminal (beta phase) $t_{1/2}$, will be calculated. A semi-parametric model described by Lee et al⁴⁰ will be used to calculate the terminal $t_{1/2}$. Other parameters will be calculated using a standard noncompartmental approach. Descriptive statistics will be reported for each parameter and will include mean \pm standard deviation and median \pm interquartile range.

The evaluation of the primary endpoint is descriptive, but 95% confidence intervals will be calculated as appropriate.

There will be a formal Statistical Analysis Plan (SAP) completed prior to database lock.

Dalcinonacog alfa_DLZ-201 VERSION 2.0, Amendment 1

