10.1.9 Protocol Amendments

Sponsor may amend the protocol as needed to ensure that the clinical investigation is being conducted as intended. Sponsor will initiate protocol amendments in writing if any change significantly affects the safety of subjects, the scope of the investigation, or the scientific quality of the study. Protocol changes must be submitted to the IRB/IEC as a protocol amendment. If necessary, the ICF and assent form will be revised to reflect the changes in the amendment and will be submitted to the IRB/IEC for review and approval. A copy of the amendment must be signed by the Investigator and returned to Sponsor or designee. Written documentation of IRB/IEC approval is required before the amendment is implemented. Investigators may not perform study-specific assessments that are not included in the protocol unless agreed to by Sponsor. Additionally, a site-specific amendment and revised ICF and assent form must be generated and submitted for approval to the IRB/IEC.

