APPENDIX B – DETAILED STUDY SCHEMA

SCREENING

Up to 4 weeks prior

Screening

- Obtain informed consent
- Review demographic parameters
- Conduct a joint evaluation as per the SOC at hemophilia treatment center
- Screen potential subjects by inclusion and exclusion criteria
- Obtain medical and hemophilia history, document
- Check vital signs, height and weight
- Conduct physical examination, check for clinical signs of thrombosis
- Conduct testing for hematology and chemistry, coagulation assay, thrombogenicity markers, immunogenicity assays, genotyping and ECG

Dalcinonacog alfa_DLZ-201 VERSION 2.0, Amendment 1

Treatment – 28 days	
Day 1 Pre-IV Dose – 5 min	Day 1

• Evaluate concomitant medications, check vital signs, and weight• Conduct physical examination, check for clinical signs of thrombosis• Conduct testing for hematology and chemistry, thrombogenicity markers, PK sampling• Conduct study subject diary training	
Day 1 IV Dose Followed by SC Dose; Day 2 to Day 28 SC Dose	Day 1

• Day 1: Administer single IV 70 IU/kg loading dose of Dalcenonacog alfa• Day 1: 30 minutes later administer SC 140 IU/kg dose of Dalcenonacog alfa• Day 2 to 28: Administer SC 140 IU/kg dose of Dalcenonacog alfa	
Post-Dose SC Dose – (30 min and Hr 7)	Day 1

• Evaluate concomitant medications and check vital signs• Conduct physical examination, check for clinical signs of thrombosis• Conduct testing for thrombogenicity markers, PK sampling• Diary entry of bleeding episodes, AEs, injection site assessment• Check for AEs• Conduct platelet count only on Day 1, Hour 7	
24 Hours Post-SC Dose	Day 2

• Evaluate concomitant medications and check vital signs• Conduct physical examination, check for clinical signs of thrombosis• Conduct testing for thrombogenicity markers, PK sampling• Diary entry of bleeding episodes, AEs, injection site assessment• Check for AEs	
Pre-SC Dose	Days 7, 14, 21, 28

• Evaluate concomitant medications and check vital signs• Conduct physical examination, check for clinical signs of thrombosis• Conduct testing for hematology and chemistry, thrombogenicity markers, PK sampling, immunogenicity assays• Diary entry of bleeding episodes, AEs, injection site assessment• Check for AEs	

Dalcinonacog alfa_DLZ-201 VERSION 2.0, Amendment 1

Washout Period - Days 29, 30, 31, 32, 33

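### The promised required dose for steady-state FIX above 12%, with a 95% CI, cannot be estimated from one fixed SC level; the SAP drops it without record and leaves the primary count untied to steady state

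*Protocol*

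**What the plan says.** All references to the protocol are to version 2.0, Amendment 1.

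- **Objective.** Protocol 3.1: "To evaluate the dose required to achieve steady-state FIX levels >12% of a SC prophylaxis treatment regimen of CB2679d". The synopsis (1.1) and SAP 3.1 agree.
- **Promised output.** Protocol 9.1, with the same sentence in the synopsis: "The dose required to achieve steady-state levels >12% will be reported for daily dosing, including 95% confidence intervals".
- **Sample size.** Protocol 9.2: "6 subjects are sufficient to provide guidance on range of dose required to achieve steady-state activity >12" per cent. The same sentence adds the starting SC dose of later studies as a use. SAP 3.5 repeats both.
- **Design.** Protocol 4.1, 6.1.2 and 8.1.2.2, and SAP 3.3 and 3.7, give each subject one IV load and then one fixed daily SC level of 100 IU/kg to Day 28. Appendix B differs: "Day 2 to 28: Administer SC 140 IU/kg dose of Dalcenonacog alfa".
- **Primary endpoint.** Protocol 9.1 and 9.4.2 and SAP 4.1 count subjects who reach a steady-state level above 12% on daily dosing. On precision, protocol 9.4.1 says: "The evaluation of the primary endpoint is descriptive, but 95% confidence intervals will be calculated as appropriate".
- **SAP primary analysis.** SAP 8.1 opens with the steady-state endpoint and lists the FIX samples, including the one about 35 minutes after the IV load. It then summarises the number and percentage of subjects above 12% during the treatment period. Tables 14.2.1.1 and 14.2.1.2 carry titles without a steady-state condition.
- **Recorded changes.** SAP 13 lists two endpoints moved to safety, the PK and PD population definitions, and the PK parameters that cannot be derived.

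**The concern.** The primary objective, the promised interval and the only rationale for six subjects all concern a dose. The design varies no dose, and the SAP analyses no dose. As written, the report would either leave its primary objective unanswered or answer it with a projection whose model is chosen after the data are seen. That figure is meant to inform the starting dose of later studies.

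The second gap concerns what is counted. If the primary tables are programmed from the summary sentence in SAP 8.1, one reading above 12% at any treatment-period sample qualifies a subject, including a reading that comes mainly from the IV load. That is a different quantity from the stated endpoint.

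**Working it through.** **1. The plan's own figure.** Six subjects. No alpha, power, effect size or standard deviation is given, and protocol 9.2 says no formal calculation is needed. The figure cannot be reproduced, and it cannot be called wrong.

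**2. Can the design estimate a required dose?** Write log(activity) = a + b·log(dose). With six subjects at one dose, the columns for intercept and log dose are proportional, so the design matrix has rank 1 for 2 parameters. The required dose would be (dose given) × (12/C)^(1/b), where C is the steady-state level observed. The data inform C but not b. Setting b = 1 (proportionality) gives an answer and an interval, but b is then assumed.

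**3. Is the assumption or the analysis stated anywhere?**

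- Protocol 9.4.1 and 9.4.2: PK parameters, descriptive statistics and the count above 12%.
- SAP 8.1 and 8.3: counts above 12%, 30% and 50%.
- SAP 9 and 9.2: compartmental and non-compartmental PK; clearance, volume, half-life and highest activity.
- SAP 9.4: when steady state is reached.
- SAP 17: no required-dose table.
- SAP 13 and the visible rows of the Note to File: no mention.

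Clearance could feed a projection, but no projection step, linearity assumption or CI method is given.

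**4. What the primary proportion can show.** 95% intervals for r out of 6:

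| r/6 | Wilson | Exact |
|---|---|---|
| 6/6 | 61.0–100% | 54.1–100% |
| 5/6 | 43.6–97.0% | 35.9–99.6% |
| 4/6 | 30.0–90.3% | 22.3–95.7% |

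**5. Which pre-dose visits represent SC steady state?** Assume one compartment and half-lives of 63.2 h to 103 h (protocol 2.2.2). At pre-dose on day d, the fraction of the IV load remaining is 0.5^(24(d−1)/half-life), and the fraction of SC steady state reached is 1 minus that.

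| Day | SC steady state reached (63.2 h; 103 h) | IV load remaining |
|---|---|---|
| 3 | 41%; 28% | 59%; 72% |
| 7 | 79%; 62% | 21%; 38% |
| 14 | 97%; 88% | 3%; 12% |
| 21 | 99.5%; 96% | 0.5%; 4% |
| 28 | 99.9%; 98.7% | 0.1%; 1.3% |

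For example, Day 21 at 103 h: 0.5^(480/103) = 0.040.

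**6. Could the SAP 9.4 test choose the visits?** It takes the first non-significant contrast as the point of steady state. I checked its power in the same model with these inputs:

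- the main-text doses, 50 IU/kg IV and 100 IU/kg SC;
- SC bioavailability of 18.2% to 23.6% (protocol 2.2.2);
- an assumed within-subject SD of 0.2 on the log scale;
- a paired contrast of one visit against the mean of the k later visits, with standard error 0.2·√(1+1/k)/√6 on 5 df.

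Power to detect that a visit still differs from the later ones:

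- Half-life 63.2 h: Day 3, 0.14 to 0.49; Day 7, 0.06 to 0.10.
- Half-life 103 h: Day 3, 0.92 to 0.99; Day 7, 0.37 to 0.52.

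So the test may well declare steady state at Day 7 or earlier, while 21% to 38% of the load remains at Day 7. It should not select the visits.

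**The case against.** **The study is descriptive, and a projection is feasible.** Both are true. Under assumed linear PK a dose could be scaled from each subject's trough or derived from clearance. A reader might infer that a required dose is impossible to obtain; the documents do not support that. The defect is an unstated assumption, an unstated method and an unrecorded omission.

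**The method may exist elsewhere.** Table shells are in a separate document, and the sponsor performs the PK analysis, so a projection could sit in a plan not seen here. That limits this point to the visible text. It does not explain the silence of SAP 13.

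**Steady state is not ignored.** SAP 4.1, the opening of 8.1, section 9.4 and Tables 14.2.3.1 and 14.2.3.2 all address it. The gap is that the summary sentence and the primary tables are not linked to them.

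**The missing interval is a smaller point.** Protocol 9.4.1 asks for intervals only where appropriate. Even so, SAP 7.4 gives a Wilson interval to a history item and SAP 8.1 gives none to the primary proportion.

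**Two stronger readings fail.**

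- Protocol 2.2.2 says the IV load "resulted in greater activity levels than simple addition of SC to IV activity", from which a reader might infer that SC dosing is non-linear. That observation concerns adding a load, in two subjects who both developed neutralizing antibodies. It does not test SC dose proportionality. It is enough that proportionality is neither stated nor justified.
- From "The nadir activity after IV plus SC dosing was 20% in both subjects in cohort 6" a reader might infer that counting any level would have misclassified those subjects. Their levels then rose above 30%, so both exceed 12% under either rule.

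**Conclusion.** The point stands as a should-fix. One planned SC level cannot yield the promised dose and interval without an assumption that is nowhere visible, and the SAP keeps the objective while omitting the analysis and the record of its omission. This follows from the design and the text and needs no numerical assumption.

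The primary count, as worded, is also not the endpoint as defined. No misclassification is shown; the wording only permits it.

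The k/6 intervals follow from the sample size alone: even 6/6 leaves a lower limit of 61.0% (Wilson) or 54.1% (exact). The steady-state fractions rest on one-compartment kinetics and the half-lives in protocol 2.2.2. The power figures rest in addition on the assumed log SD of 0.2. A reader might want to know how far a projected dose could be off. The documents give no basis for that, because any figure would rest on an assumed exponent and on a cohort given a different SC dose.

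**What to change.** 1. **Objective.** In protocol 1.1, 3.1, 9.1 and 9.2 and SAP 3.1 and 3.5, state the aim as estimating the proportion of subjects with steady-state FIX activity above 12% on the single tested daily SC regimen, and remove the required-dose interval. Alternatively, keep a projected dose as exploratory only, with the dose-proportionality assumption and the CI method fixed in advance. Record the choice in SAP 13.
2. **Primary tables.** Base Tables 14.2.1.1 and 14.2.1.2 on fixed late pre-dose troughs, for example Days 21 and 28, with a subject-level rule such as all available selected troughs above 12%. Keep the SAP 9.4 test as supportive only.
3. **Precision.** Add a Wilson or exact 95% CI to that proportion.
4. **Regimen.** Appendix B gives IV and SC levels that differ from protocol 6.1.2 and 8.1.2.2 and SAP 3.7. These passages must be reconciled so that the tested regimen is unambiguous.

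**Cost.** The stated objective becomes more modest, and the count above 12% may be lower than under an any-level rule. The protocol wording needs an amendment, since "Protocol changes must be submitted to the IRB/IEC as a protocol amendment". In the SAP the work is a section 13 entry, a sample-selection rule and one interval in two tables. Data collection does not change.

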9.2 SAMPLE SIZE DETERMINATION

6 subjects are sufficient to provide guidance on range of dose required to achieve steady-state activity >12% and starting SC dose for subsequent studies. As this study is not inferential, no formal sample size calculation is required.

9.3 POPULATIONS FOR ANALYSES

Safety population: any patient who receives at least one dose.

Efficacy/PD population: any patient who receives at least one week of daily SC dosing and PK specimens obtained.

If a subject does not complete the study as defined in the protocol another subject will need to be enrolled in replacement.

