7. STUDY INTERVENTION DISCONTINUATION AND PARTICIPANT DISCONTINUATION/WITHDRAWAL

7.1 PARTICIPANT DISCONTINUATION/WITHDRAWAL FROM THE STUDY

Subjects are free to withdraw from participation in the study at any time upon request.

An investigator may discontinue or withdraw a participant from the study for the following reasons:

- Significant study intervention non-compliance
- If any clinical AE, laboratory abnormality, or other medical condition or situation occurs such that continued participation in the study would not be in the best interest of the participant
- If the participant meets a criterion (either newly developed or not previously recognized) that precludes further study participation
- Decision by Investigator or Sponsor

The reason for participant discontinuation or withdrawal from the study and the date will be recorded on the eCRF.

Replacement of a subject occurs for the following reason:

- If a subject does not complete 21 days of daily SC dosing, as defined in the protocol, another subject may be enrolled.

If the subject withdraws from the study and also withdraws consent for disclosure of future information, no further evaluations should be performed, and no additional data should be collected. The sponsor may retain and continue to use any data collected before such withdrawal of consent.

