5.2. Safety Population

The Safety Population will include all subjects who were administered at least one dose of study medication. Subjects will be analyzed according to treatment received. The Safety Population will be used for all analyses of efficacy in respect to PK and PD and safety endpoints and for the presentation of subjects in subject listings.

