5.3. Pharmacokinetic (PK) Population

The PK population is defined as any subject who was administered at least one week of daily SC dosing and had FIX activity values at four or more time points. The PK data will be listed for this population and used in all PK analyses. The PK data for subjects with protocol deviations affecting the results may be excluded from summaries and analyses. Any protocol deviations pertaining to the validity of PK analyses (and thus inclusion in the PK population) will be determined before the database lock based on a review of all protocol deviations.

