6.3. Missing Data

Missing data will not be imputed in this study. All analyses will be based on available data.

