8.1. Primary Efficacy Endpoint and Analysis

The primary endpoint is the number and percentage of subjects who achieve a steady-state FIX activity level above 12% with daily dosing.

On Day 1, FIX activity level will be assessed at pre-IV dose and repeated 35 (+/- 5) minutes later prior to the SC dose. Subsequent FIX activity assessment will be performed pre-dose on days 2, 3, 7, 14, 21 and 28, and during washout period on days 29, 30, 31, 32, and 33.

Number and percentage of subjects and list of the subjects with a FIX activity level >12% will be summarized during treatment period for the PK and the Safety Population.

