15.2.5.2. Table Conventions

Units will be included where available

If the categories of a parameter are ordered, then all categories between the maximum and minimum category are presented in the table, even if n=0 for all treatment groups in a given category that is between the minimum and maximum level for that parameter. For example, the frequency distribution for symptom severity would appear as:

Severity Rating	N
severe	0
moderate	8
mild	3

Where percentages are presented in these tables, zero percentages will not be presented and so counts of 0 will be presented as 0 and not as 0 (0%).

If the categories are not ordered (e.g., Medical History, Reasons for Discontinuation from the Study, etc.), then only those categories for which there is at least 1 subject represented in 1 or more groups are included.

This document is confidential.

Statistical Analysis Plan for Interventional Studies
Sponsor: Catalyst Biosciences, Inc.; Protocol No.: DLZ-201

An Unknown or Missing category are added to each parameter for which information is not available for 1 or more subjects.

Unless otherwise specified, the estimated mean and median for a set of values are printed out to 1 more significant digit than the original values, and standard deviations are printed out to 2 more significant digits than the original values. The minimum and maximum should report the same significant digits as the original values. For example, for systolic blood pressure:

n	XX
Mean (SD)	XX.X (xx.xx)
95% CI	XX.X - XX.X
Median +/- IQR	xx.xx +/- xx.xx
Min - Max	xx.x - xx.x

Percentage values are printed to one decimal place, in parentheses with no spaces, one space after the count (e.g., 7 (12.8%), 13 (5.4%)). Display values that round down to 0.0 to 0.0. Unless otherwise noted, for all percentages, the number of subjects in the analysis set for the treatment group who have an observation will be the denominator. Percentages after zero counts should not be displayed and percentages equating to 100% are presented as 100%, without decimal places.

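### The two replacement rules conflict, and no rule makes a subject who stops early for an antibody or loss of activity count as not achieving steady-state FIX above 12%

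*Protocol*

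**What the plan says.** **Replacement.** Protocol 9.3: "If a subject does not complete the study as defined in the protocol another subject will need to be enrolled in replacement". Protocol 7.1: "If a subject does not complete 21 days of daily SC dosing, as defined in the protocol, another subject may be enrolled". SAP 5.1 repeats the 7.1 rule and does not mention the 9.3 rule. SAP 13, which lists changes from the protocol, is silent on it. Neither rule depends on the reason for stopping.

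**Sample size.** Six subjects are planned, with no allowance for dropout or replacement: "As this study is not inferential, no formal sample size calculation is required".

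**Primary endpoint.** The endpoint is the number of subjects reaching a steady-state FIX activity above 12%. The analysis sentence in SAP 8.1 says that subjects with a "FIX activity level >12% will be summarized during treatment period for the PK and the Safety Population". It does not repeat the steady-state condition, and neither do the titles of Tables 14.2.1.1 and 14.2.1.2. It does not say whether the count is by visit, at a late visit or at any time.

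**Populations.** "The Safety Population will include all subjects who were administered at least one dose of study medication". The PK Population needs "at least one week of daily SC dosing and had FIX activity values at four or more time points".

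**Denominator and missing data.** Unless otherwise noted, "the number of subjects in the analysis set for the treatment group who have an observation will be the denominator" (SAP 15.2.5.2). SAP 6.3 adds: "Missing data will not be imputed in this study. All analyses will be based on available data".

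**The concern.** Stopping in this trial may well be linked to the outcome. Clinical evidence of an inhibitor and laboratory signs of an antibody are both grounds for interrupting dosing (Protocol 4.1 and 6.1.2.1). Protocol 2.2.2 reports that both earlier-study subjects given an IV load followed by SC dosing developed neutralizing antibodies, transiently in one. A subject who stops for that reason has not shown a sustained level above 12%, and the primary result should show it.

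The plan does not guarantee this. Replacement refills the planned six, and the primary table has no rule that makes the original subject a non-achiever. With six subjects, one person's classification moves the percentage by 14 points or more. The result is meant to guide the starting SC dose of later studies.

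**Working it through.** **1. The two rules applied to the same subject**

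| Subject | Protocol 7.1 and SAP 5.1 | Protocol 9.3 |
|---|---|---|
| Stops dosing before 21 days and leaves | May be replaced | Must be replaced |
| Stops dosing on Days 21 to 27 and leaves | No replacement | Must be replaced |
| Takes all 28 SC doses, misses End of Study | No replacement | Must be replaced |

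The rules disagree in every row: on force in the first, and on trigger in the other two.

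**2. Which population an early stopper falls in**

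Scheduled FIX samples in the treatment period are Day 1 pre-IV, Day 1 post-IV, and pre-dose on Days 2, 3, 7, 14, 21 and 28. Assume that every scheduled sample up to the last dosing day is taken.

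| Last dosing day | FIX values | Pre-dose values after Day 1 | PK Population | Steady-state model (at least 3 of 6 pre-dose values, SAP 9.4) |
|---|---|---|---|---|
| 2 | 3 | 1 | No | No |
| 3 to 6 | 4 | 2 | No (under one week) | No |
| 7 to 13 | 5 | 3 | Yes | Yes |
| 14 to 20 | 6 | 4 | Yes | Yes |
| 21 to 27 | 7 | 5 | Yes | Yes |

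Everyone dosed is in the Safety Population. The first on-treatment antibody sample is at Day 7, so a subject stopped for a laboratory-detected antibody would usually be in both populations.

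**3. Two readings of SAP 8.1 for that subject**

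- *Late-visit or by-visit table.* He has no Day 21 or Day 28 value. Under SAP 6.3 and 15.2.5.2 he is not in that percentage's denominator, even in the Safety Population table.
- *Any value above 12% during treatment.* He stays in the denominator, and one early value makes him a success. SAP 8.1 lists the Day 1 post-IV sample among its assessments and does not exclude it. Early values above 12% are plausible: Protocol 2.2.2 gives a nadir of 20% in both earlier subjects after IV plus SC dosing, although that cohort's regimen is in a figure not available here.

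Neither reading makes him a non-achiever as a matter of rule.

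**4. Illustration of size**

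The documents give no dropout or response rate, so these are assumed cases: six completers all above 12%, plus one or two replaced subjects who stopped early for an antibody or loss of activity. Limits are exact (Clopper-Pearson) 95% limits, because no interval method is named for this endpoint. When x = n the lower limit is 0.025^(1/n), for example 0.025^(1/6) = 54.1%.

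| Counting rule | One early stopper | Two early stoppers |
|---|---|---|
| Late visit, observed only | 6/6 = 100% (54.1 to 100) | 6/6 = 100% (54.1 to 100) |
| Any value, early values above 12% | 7/7 = 100% (59.0 to 100) | 8/8 = 100% (63.1 to 100) |
| All dosed, stopper a non-achiever | 6/7 = 85.7% (42.1 to 99.6) | 6/8 = 75.0% (34.9 to 96.8) |

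The differences are 100 − 85.7 = 14.3 points and 100 − 75 = 25 points.

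**5. How likely is at least one early stop?**

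For an assumed rate p per subject, the chance is 1 − (1 − p)^6: 26.5% at p = 5%, 46.9% at 10% and 73.8% at 20%.

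**The case against.** The best defence is that nothing removes a replaced subject from the analysis. The Safety Population keeps everyone dosed, and the primary endpoint is tabulated there as well as in the PK Population. Discontinuations with reasons (SAP 7.1) and exclusions from populations (SAP 5.5) are tabulated, and FIX and antibody results are listed for all dosed subjects. SAP 15.2.5.2 also adds an unknown or missing category, and SAP 15.2.4 puts the population size in the headings. The observed-only denominator is a default, the table shells are in a separate document, and the study is descriptive.

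All of this stands, and it rules out three stronger conclusions that a reader might draw:

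- *That replaced subjects disappear from the report.* They do not, for the reasons above.
- *That antibody stoppers generally leave the PK Population.* Those stopping from Day 7 onward normally qualify. The loss mainly affects stops within the first week. A Day 6 draw inside the visit window, or an exclusion for a protocol deviation, would be exceptions.
- *That replacement dilutes the antibody findings.* Antibody results use the Safety Population. Antibody formation is an event of special interest with its own table, and dosed subjects must be followed after withdrawal (Protocol 8.4.4). Replacements who were dosed and tested belong in that denominator.

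It is also true that the replacement conflict does not cause the counting problem; settling one leaves the other. And treating every adverse-event stop as a failure would misclassify a subject who already had steady-state troughs above 12%.

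The defence does not supply the missing rule. Being in a population is not the same as being in a percentage's denominator. A missing row shows that a value is absent, but does not count the subject as a non-achiever. The any-time reading keeps him only by allowing an early value to count as success.

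**Conclusion.** There are two separate defects. First, the replacement rules contradict each other in trigger and force, and must be reconciled; until then the number to be enrolled is not fixed. This rests on the text alone.

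Second, the primary-endpoint analysis does not ensure that a subject who stops early for an antibody or loss of activity counts as not achieving steady-state FIX above 12%. The direction favours the drug: he is either left out or can be counted as a success.

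The size depends on events that the documents do not predict. The contrast of 100% (6/6) with 75% (6/8) assumes a late-visit table and two such stoppers. With one, the contrast is 100% with 85.7%. Neither is a forecast, and with no such stopper there is no difference. The intervals are wide and overlap throughout, so what is at risk is the headline count in a small descriptive study. The point should be fixed, but it does not invalidate the trial.

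**What to change.** 1. **Replacement.** State one rule, with one trigger and one force, in Protocol 7.1, Protocol 9.3 and SAP 5.1. Which rule to keep is for the sponsor and investigator to decide. Add that replaced subjects stay in all summaries.
2. **Denominator.** In SAP 8.1, make all dosed subjects, including replaced ones, the denominator for the main primary-endpoint table. The default in SAP 15.2.5.2 already allows a noted exception. The PK Population table can remain as support.
3. **Counting rule.** In SAP 8.1, say which pre-dose values count as steady-state troughs. Count as non-achievers those who stop for antibody formation or loss of activity, and those who stop before any steady-state trough is available. Classify a subject who already has steady-state troughs above 12%, and stops for an unrelated adverse event, on those troughs.

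The cost is protocol and SAP wording, with no extra subjects or samples. The downside is that the reported percentage may be lower.
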